Applications of dual energy CT for improving staging and monitoring of therapy response in patients with osseous metastases from castrate-resistant prostate cancer

DUKE CANCER INSTITUTE

A National Cancer Institute-designated Comprehensive Cancer Center

Sponsor: PI – Duke Cancer Institute
Funding Source: Society of Abdominal Radiology
Protocol Source: PI - Duke Cancer Institute
Duke IRB#: Pro00078046

Principal Investigator

[name], M.D.
Dept of Radiology
[name]
[name]
[name]
[name]
Fax

[contact]

Co-Principal Investigator(s)

Name, degree
Email address

Sub-Investigator(s)

[name], MD PhD
[contact]
[name], MD, MBA
[contact]

Statistician

[name],
Ph.D.
[contact]

Lead Study Coordinator

Name, degree TBS
Email address

Regulatory Coordinator

[name].
[contact]

Data Manager

Name, degree
Email address

Original version: Date 10/10/2016

Amended version Date
1:

Protocol Title:

Pilot study to assess feasibility of using dual energy CT to improve staging and monitoring of therapy response in patients with osseous metastases from castrate-resistant prostate cancer.

Short Title:

Dual energy CT for improving staging and monitoring of therapy response in patients with castrate-resistant prostate cancer.

Purpose of the Study:

To evaluate the capabilities of dual energy CT as a more precise and accurate tool for staging and monitoring of therapy response in patients with osseous metastases from castrate-resistant prostate cancer.

Our working hypothesis is that, by providing quantitative material-specific information of tissue composition, dual energy CT may yield more accurate and precise quantitative information for the staging and monitoring of therapy response in patients with osseous metastases from castrate-resistant prostate cancer. State of the art dual-energy MDCT technology, which is available and routinely utilized at Duke University, relies on simultaneous acquisition of two CT datasets at different energy levels, without increasing patient radiation exposure. The dual energy datasets can be used to calculate conventional CT images, similar to a routine single energy CT acquisition, or they can be further processed to extract material-specific information. The latter datasets have proven to be beneficial in multiple clinical scenarios (2-4).

Patients with osseous metastases from prostate cancer provide a common clinical and diagnostic challenge. Not uncommonly, subclinical metastatic lesions may only become detectable at imaging in response to therapy due to increased bone deposition during the first three months of post therapy. Commonly used imaging tests (such as CT or bone scan) are unable to reliably differentiate this phenomenon (also referred to as “flare”) from progressive metastatic osseous disease. This diagnostic challenge may have profound negative effects on patient management as it will require multiple additional imaging follow-up studies before an accurate assessment of tumor response can be formulated with appropriate management (Prostate Cancer Clinical Trials Working Group 3 [PCWG3]).

We postulate that dual energy CT may provide additional critical information in this clinical scenario. Specifically, by providing material-specific quantitative information on iodine concentration within tissues, dual energy CT may be able to distinguish between iodine uptake within viable metastatic osseous disease and lack of thereof within treatment-related reactive sclerotic lesions. This differentiation may not be possible using conventional attenuation measurements with single-energy CT due to the challenging anatomical environment within the

vertebral body where sclerotic metastatic tissue coexists with the complex structural anatomy of the fine trabecular bone.

Background & Significance:

Prostate cancer (PCA) is the most frequently diagnosed cancer in North America. It is the fourth most common cause of cancer death overall and the third most common cause of cancer death in men. In this cancer, bone represents a preferential site of metastases, and patients with advanced disease have a very high incidence of bone metastases. Autopsy data from prostate cancer patients indicate an incidence of secondary bone lesions as high as 65–75%, preceded only by multiple myeloma. These bone metastases are typically osteosclerotic (i.e. with increased osteoblastic activity), and likely to produce a significant impact on patients' functional status and quality of life, not only related to pain, but also to the relevant risk of skeletal-related events that can negatively impact physical well-being and activities of daily living.

Castrate-resistant PCA presents a spectrum of disease ranging from rising prostate-specific antigen (PSA) levels in the absence of metastases or symptoms and despite androgen-deprivation therapy, to metastases and significant debilitation from cancer symptoms. Castrate-resistant PCA is usually suspected in patients with new symptoms on androgen deprivation therapy, with a rising PSA, or with new evidence of disease on bone scans or CT scans.

Novel hormonal agents such as abiraterone acetate and enzalutamide improved survival significantly for patients with metastatic castration-resistant prostate cancer. Nevertheless, median survival is limited to 35 months after initiation of therapy. Therefore, it is beneficial to have a more accurate diagnostic measure to assess time to progression, either for patients to receive optimal therapy regimes or for studies to have a more accurate time to progression measure (5, 6). For this reason, the PCWG3 defined criteria for progression of the disease. The most challenging task is the assessment of bone metastases in the early phase of therapy due to common onset of a flare phenomenon. The flare phenomenon refers to the increase in radiotracer uptake at previously diagnosed or new previously undetected lesions soon after initiating therapy. Increased uptake is transient, but variable, lasting between three and six months. It is thought that the increase is a response to bone deposition and repair at treated sites. This increase in signal makes the distinction between progression of bone lesions or increased metastatic spread and successful treatment considerably difficult. In CT scans these lesions would appear osteosclerotic and thus could not be distinguished between therapy response and progression. For this reason, the PCWG3 defined progression as “appearance of at least two new lesions on first post-treatment scan, with at least two additional lesions on the next scan (2+2 rule). If at least two additional new lesions are seen on the next (confirmatory) scan, the date of progression is the date of the first post-treatment scan, when the first two new lesions were documented.” This implicates that progression needs to be dated back and diagnosis of progression is delayed by three months typically.

This highlights the critical need to precisely and accurately determine between flare and progressive disease after onset of therapy.

State of the art dual-energy CT enables simultaneous acquisition of two CT datasets at different energy levels *without* exposing patients to additional radiation dose. These datasets can be used to reconstruct regular CT images of identical image quality compared to conventional single-energy CT or facilitate further processing of dual-energy material-specific density images. Preliminary evidence suggest that material density images may improve detection of lithic metastatic lesions, such as in patients with multiple myeloma (7). However, the diagnostic accuracy of material density analysis in patients with sclerotic osseous metastases (such as patients with PCA) remains to be investigated. This is a particularly challenging task due to bone mineral deposition within primarily osteosclerotic metastatic lesions, remodeling of bone due to therapy response, and the complex structural anatomy of the trabecular bone within the vertebral bodies.

Our working hypothesis is that, by providing quantitative material-specific information of tissue composition, dual energy CT may yield more accurate and precise quantitative information for the staging and monitoring of therapy response in patients with osseous metastases from castrate-resistant prostate cancer.

Purpose of this study

Primary Objective:

Demonstrate the feasibility of using dual energy CT to improve staging and monitoring of therapy response in patients with osseous metastases from castrate-resistant prostate cancer, compared to regular single energy CT and technetium bone scans.

Secondary Objectives:

Analyze the feasibility to detect bone metastasis at baseline more accurately.

Analyze iodine uptake of soft tissue metastasis more accurately and monitor its change during therapy.

Correlate whether iodine quantification is a viable biomarker for early detection (small size) of lymph node metastases.

Exploratory Objective:

Determine whether dual energy CT is able to have prognostic capabilities in terms of therapy response and overall survival.

Design & Procedures:

This is a prospective Health Insurance Portability and Accountability Act-compliant study for which we are asking for authorization from the Institutional Review Board.

Inclusion Criteria:

1. Oncology patients with castrate-resistant prostate cancer planned for therapy with abiraterone acetate or enzalutamide and prednisolone undergoing clinically indicated MDCT of the chest, abdomen and pelvis
2. > 18 years old
3. Serum creatinine < 2.0
4. BMI < 35kg/m²
5. Sign informed consent

Exclusion Criteria:

History of anaphylactoid reaction to iodinated contrast material

All MDCT examinations will be performed using a third-generation dual-source dual-energy MDCT platform (Somatom Definition FORCE, Siemens Healthcare, Forchheim, Germany). Each patient will receive an unenhanced dual energy scan followed by a contrast-enhanced dual energy scan as part of clinical routine work up (Table 1). The preliminary unenhanced dual energy scan, which is currently *not* part of our routine clinical protocol, will provide necessary information for the baseline material density quantitative analysis of the bone marrow. For the contrast-enhanced scan, each patient will be scanned in a caudocranial direction during the hepatic venous phase 60-70 seconds after the start of contrast medium injection. No change in the contrast material injection protocol will be performed for this study.

Patients will be examined with a dual-energy protocol at baseline (i.e., before starting therapy), and during the first and second follow up scans in order to differentiate between patients with partial remission, stable, or progressive disease.

Table 1. Details of the dual-energy CT scan protocols.

		kVp	Pitch	Effective mAs	mAs / rotation	Relative CTDI _{vol} (%)	Relative DLP (%) [*]
1st scan	Tubes 1 + 2	120	1	200	200	100	100
	Tube 1	100	1				
	Tube 2	150	1				
2nd scan	Tubes 1 + 2	120	1	200	200	100	100
	Tube 1	100	1				
	Tube 2	150	1				

Images will be reconstructed following conventional protocols and will include 5.0 and 0.6 mm slice thickness using filtered back projection (FBP) and commercially available iterative reconstruction (advanced modeled iterative reconstruction algorithm [ADMIRE]).

In addition, we will collect relevant clinical and demographic patient's information, such as prostate cancer related parameters, medical record number, age, gender, and body weight, height and body mass index. We will also collect information regarding the CT parameters, radiation dose and image quality.

For part of this investigation we will use commercially available dual-energy CT postprocessing software (SyngoVia VB10, Siemens Helathcare, Forchheim, Germany). At the same time, we will also be working in collaboration with Siemens Healthcare as part of study Pro00078046. Selected and fully anonymized image datasets in dicom format or raw-projection format will be shared with Siemens scientists for the purpose of developing postprocessing software which will be used in the study. While existing dual-energy CT software can be used to separately analize the pre and postcontrast phases, we will work in collaborations with Siemens to elaborate strategies and potentially dedicated prototype software which will register the image datasets and perform advanced dual-energy CT postprocessing.

All reconstructed CT datasets will be stored on a dedicated and password-protected server in the Department of Radiology. The image reconstruction process will take place within the radiology department on a radiology owned and maintained workstation.

Selection of Subjects:

1. Subject Recruitment and Compensation:

Consent Process:

One hundred and fifty eligible participants will be contacted via mail by their attending oncologist (Dr. [name]) prior to their clinically indicated CT scan. The study coordinator will consent eligible participants according to the inclusion criteria provided in the Design & Procedure section. If necessary, the participants will have no less than 24 hours to consider their participation. Consenting will take place in a private room. The prospective participant may have family or a friend present during the consent process, if they wish. At least an hour will be slotted for the consent process, but we will not prevent the subject from asking questions beyond that time. If the subject wishes to consider the study overnight or longer, an additional appointment will be made for the subject to continue the consent process. From the time of initial contact until the participant completes the study they will have complete freedom to access the coordinator by phone, email or in person. Each patient is given the possibility to refrain from the study after the baseline scan or the first follow up examination without any disadvantage regarding clinical treatment or imaging.

[figure not shown]
There will be no financial compensation for participation to this study.

Subject's Capacity to Give Legally Effective Consent:

Subjects without capacity to give consent will not be recruited in this study.

2. Study Interventions:

The diagnostic scan will be preceded by a not clinically indicated non enhanced dual energy scan. The overall radiation dose to the patient for the first and second acquisition will be twice the radiation dose of a conventional CT of the chest, abdomen and pelvis.

3. Risk/Benefit Assessment:

The contrast-enhanced CT scan of the chest, abdomen and pelvis will be performed according to the clinical indication of castration-resistant prostate cancer, as determined by the referring oncologist.

This initial diagnostic scan will be preceded by an unenhanced dual energy scan, which is currently *not* part of our routine clinical protocol. This preliminary scan will provide the necessary information for the baseline material density quantitative analysis of the bone marrow. A second acquisition following intravenous contrast medium administration will be performed thereafter. Our protocol will result in a twofold increase in overall radiation dose to the patient compared to a routine conventional CT of the chest, abdomen and pelvis. This protocol will be repeated at baseline, first and second follow up resulting in three

additional CT scans in total and a cumulative additional radiation exposure of approximately 30mSv. This increase in radiation dose is not outside the standard of care as multiphasic MDCT examinations which include pre-, post-contrast imaging are routinely performed, even in young patients without cancer, for the work-up of indeterminate liver, renal, or adrenal lesions, as well as in patients with unexplained hematuria. Of note, many of these multiphasic CT protocols at our institution include dual-energy CT as the standard of care. Considering the demographic of PCA, we anticipate that most of our patients will consist of older age males with decreased life-expectancy. As such, the clinical implications of the marginal increase in radiation dose with our dual-energy CT protocol are favored to be negligible. Furthermore, some patients might even benefit from additional unenhanced CT scans because some secondary findings can be distinguished more precisely when additional unenhanced CT information is available.

An additional identifiable risk to the subjects is the unlikely but not impossible loss of confidentiality. We have taken all the precaution to minimize this risk. Identifiable PHI will remain with their respective CT exam on a radiology department server and on PACS. HIPAA trained Duke personnel will have access to these exams, and only HIPAA trained Duke personnel will be involved in the study. For each exam, a date, exam protocol type, patient name, and patient ID number will be recorded. Files containing these ID numbers and the dates of the exams will be kept by one of the investigators on a password-protected computer.

4. Costs to the Subject:

There will be no cost to the patients entered in the study.

5. Data Analysis & Statistical Considerations:

All image data will be processed using either commercially available software (SyngoVia VB10) or software prototypes developed for dual-energy CT postprocessing. All study data will be analyzed at Duke University. However, to further develop software prototypes which will be needed for image registration and advanced dual-energy CT postprocessing, we will work in collaboration with Siemens scientists as part of project with duke id Pro00078046. This will require we share with Siemens sample datasets, which will include DICOM image series or raw-projection datasets. In all cases, we will only share fully anonymized data.

To ensure consistency and reproducibility of the data, quantitative measurements of iodine uptake will be performed on a dedicated secondary workstation unit (Core2 x6800; Intel, Santa Clara, Ca) equipped with a previously validated custom Matlab-based software (Matlab, Ver. 2009a, Math-Works, Natick, Ma). Qualitative analysis of post-processed datasets will be performed on an offline workstation equipped with Osirix (Pixmeo SARL, Bernex, Switzerland). Statistical analysis will be performed in collaboration with the department of biomedical statistics. Multi-parametric regression analysis will identify whether dual energy based, calcium corrected iodine maps a valuable biomarker for monitoring and staging of

metastatic bone disease in prostate cancer. For the specific objectives of this study we intend to perform the following analyses.

To demonstrate the feasibility to monitor metastatic bone disease in castration resistant prostate cancer more accurately than regular single energy CT, single phase dual energy CT and technetium bone scans a quantitative analysis of iodine uptake will be performed. ROC statistics will be calculated to find optimal threshold of this biomarker. Qualitative analysis will be done by multiple readers in blinded fashion to determine sensitivity and specificity for distinction between disease progression at first follow-up three month after initiation of therapy. Findings will be correlated with technetium based bone scans.

To analyze the feasibility to detect bone metastasis at baseline more accurately, unenhanced bone marrow imaging will be calculated and additional dual energy based, calcium corrected iodine maps will be used to determine a threshold for detection of vital bone metastasis in order to calculate color coded bone maps for risk of presence of bone metastases. Qualitative analysis will be done by multiple readers in blinded fashion to determine sensitivity and specificity.

To analyze iodine uptake of soft tissue metastasis more accurately and monitor its change during therapy, a ROI based analysis will be performed for suspect metastatic lesions at three time points to see effects of therapy and to distinguish between partial remission, stable disease and progressive disease. A blinded multi reader assessment of iodine maps will be performed to calculate sensitivity and specificity for qualitative analysis of dual energy based examination compared to single-energy CT.

As an exploratory objective we want to determine whether dual energy CT has prognostic capabilities when assessing bone marrow metastases and soft tissue metastasis in terms of therapy response and overall survival. This exploratory objective will require long term follow up and access to patient data exceeding the time period of the baseline and first two follow up CT examinations. Caplan Mayer curves will be drawn and correlated with findings of bone marrow analysis.

Another exploratory objective is to correlate whether adjusted iodine quantification is a viable biomarker for early detection of lymph node metastases, which are too small to fulfill RECIST criteria of a metastasis at baseline but will become evident on follow up. A ROI analysis will be performed to assess whether adjusted iodine uptake might be a viable biomarker for early detection of lymph node metastases.

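### The primary objective is feasibility, but no analysis estimates how often the two-phase iodine map can be produced and read, and exams without one have no place in the accuracy counts

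*Combined protocol and SAP*

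**What the plan says.** The Protocol Title calls the study a "Pilot study to assess feasibility of using dual energy CT to improve staging and monitoring of therapy response", and the Primary Objective repeats that aim: "Demonstrate the feasibility of using dual energy CT to improve staging and monitoring of therapy response", with single-energy CT and technetium bone scans as comparators.

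The matching paragraph of section 5 is introduced as demonstrating feasibility. It adds single-phase dual energy CT as a comparator. Its content is quantitative iodine uptake, then "ROC statistics will be calculated to find optimal threshold of this biomarker", then "Qualitative analysis will be done by multiple readers in blinded fashion to determine sensitivity and specificity for distinction between disease progression at first follow-up", then correlation with bone scans.

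On the software, Design & Procedures says that "existing dual-energy CT software can be used to separately analize the pre and postcontrast phases". For combining the phases, the collaboration is to work out strategies and "potentially dedicated prototype software which will register the image datasets and perform advanced dual-energy CT postprocessing". Section 5 is firmer and refers to "software prototypes which will be needed for image registration and advanced dual-energy CT postprocessing". No development timeline is given.

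Every patient has an unenhanced dual energy scan before the contrast-enhanced one, at baseline and at two follow-ups. Section 2 (Study Interventions) says the unenhanced scan is not clinically indicated. Section 3 (Risk/Benefit Assessment) puts the total at "a cumulative additional radiation exposure of approximately 30mSv". Image quality is collected under Design & Procedures, but no analysis uses it.

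**The concern.** Whether a method is feasible and how accurate it is when it works are separate questions. The plan estimates only the second. Its own text leaves the first open, because combining the two phases depends on software still under development.

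Three things follow. First, no stated result would show that the two-phase method is technically unworkable or workable only sometimes. Second, there is no rule for an exam whose phases cannot be registered or whose map cannot be read. Such exams can drop out of the sensitivity and specificity without comment, or the rule can be chosen once results are known. Third, no planned step tells the sponsor or IRB how often the map is obtained while research-only scanning goes on.

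**Working it through.** **1. Objective against analysis.** There is no plan figure to reproduce. The documents give no feasibility rate, success criterion, sample-size calculation or precision target. Taking the outputs of the primary paragraph of section 5 in turn:
- iodine uptake: a measurement;
- ROC threshold: discrimination;
- reader sensitivity and specificity: accuracy, with no denominator stated;
- bone-scan correlation: agreement with another test.

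None is a proportion of exams that yield a registered, readable map.

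**2. Which analysis is affected.** Section 5 names single-phase dual energy CT as a comparator. I therefore read the combined pre/post-contrast result as the index test for the primary objective. The protocol does not say so outright. Existing software covers the phases separately, and the prototypes are for registration and advanced processing. The gap lies in that combined analysis.

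**3. Exposure (section 3).** 30 mSv / 3 scans = about 10 mSv per research-only scan. If all 150 men contacted enrolled and completed, there would be 150 × 3 = 450 such scans. This is an upper bound, because the number enrolled is not stated.

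**4. Effect of leaving out unusable exams.** Let S be sensitivity among usable exams and f the unusable fraction among men with progression. Counting unusable exams as incorrect gives S × (1 − f). S = 0.85 and all values of f are assumptions.

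| f | calculation | sensitivity, all scanned |
|---|---|---|
| 5% | 0.85 × 0.95 | 0.81 |
| 15% | 0.85 × 0.85 | 0.72 |
| 25% | 0.85 × 0.75 | 0.64 |

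Specificity scales in the same way, with f taken among men without progression. If a reading needs both the baseline and the first follow-up map, and failures are independent, a 90% success rate per exam leaves 0.9 × 0.9 = 81% of men evaluable. The plan does not say whether both are needed.

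**5. What a usable-map proportion would show.** Exact (Clopper-Pearson) 95% CIs at an observed 90%: 27/30, 73.5 to 97.9%; 45/50, 78.2 to 96.7%; 135/150, 84.0 to 94.3%. The denominators are illustrative.

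**6. What 15 exams can tell.** The probability of 12 or more usable maps out of 15 is the sum over k = 12 to 15 of C(15,k) p^k (1 − p)^(15−k).

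| true success p | P(12 or more of 15) |
|---|---|
| 90% | 0.94 |
| 80% | 0.65 |
| 70% | 0.30 |
| 60% | 0.09 |

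Fifteen exams separate 90% from 60% well, but they separate 80% from 70% poorly. That supports an informative report and does not support an automatic rule.

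**The case against.** The strongest reply is that section 5 does tie an analysis to feasibility. The objective is feasibility of improving staging and monitoring against other tests, so it can fairly be read as diagnostic proof of concept, for which accuracy is a natural measure. This stands in part: a reader who inferred that no analysis is assigned to the objective would be wrong. The assigned analysis still leaves technical yield unmeasured.

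A reader might also infer that scanning starts before any registration software exists, and that failure would be learned only after all men were exposed. The documents do not establish either. They give no timeline, section 5 speaks of developing prototypes further, and Design & Procedures describes the work as concurrent. Nothing defers processing to the end, and stored datasets might be reprocessed.

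Nor is the unenhanced scan without use if registration fails. It serves the baseline bone-marrow analysis, the soft-tissue and lymph-node analyses are ROI-based, and iodine is measured with a Matlab tool described as validated. All of this stands, and it confines the point to the combined analysis.

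Two cautions on the remedy also stand. An early look may judge immature software. A per-man endpoint over all enrolled men would mix technical failure with withdrawal, which the Consent Process permits after baseline or first follow-up.

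**Conclusion.** The point holds in this form: the primary objective is feasibility, the assigned analysis measures accuracy only, and the yield of the combined two-phase map is neither estimated nor reported during the study. As written, feasibility could be concluded from successful exams alone.

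The size depends on the unknown failure rate. At assumed rates of 5 to 25%, a sensitivity of 0.85 among usable exams falls by 4 to 21 percentage points (0.85 to 0.81 and to 0.64) when all scanned men are counted. Counting failures as incorrect is one convention among several. The conclusion also rests on reading the combined map as the index test.

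A reader might take the 150 men in the Consent Process as an adequate sample for a feasibility proportion. The documents do not support that, because 150 is the number contacted. No claim about adequacy of size is made here. The change should be made.

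**What to change.** 1. Add to the primary analysis the proportion of performed two-phase exams that give a registered, readable calcium-corrected iodine map, separately for baseline and first follow-up, with exact 95% CIs. Report withdrawals and exams not done apart from technical failures.
2. Report technical success to the sponsor and IRB after about the first 15 baseline exams. This is information for their decision and not an automatic stop. The report should say that software may still be in development and that exams can be reprocessed.
3. For reader sensitivity and specificity, show a table of all scanned men with unusable exams counted as incorrect, beside the usable-only table. An unusable exam has no iodine value, so the ROC analysis stays usable-only, with the number excluded stated.
4. Give confidence intervals for all accuracy estimates.

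The cost is a short amendment, one brief early report and a little more analysis. No additional patients, scans or readers are needed. The real downside is that headline accuracy may be clearly lower once unusable exams are counted.

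### Does admitting men without bone lesions, with no stated analysis set, undermine the primary accuracy estimates?

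*Combined protocol and SAP*

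**What the plan says.** The Primary Objective is to show that dual energy CT can feasibly improve staging and the monitoring of "therapy response in patients with osseous metastases from castrate-resistant prostate cancer, compared to regular single energy CT" and technetium bone scans.

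The first inclusion criterion is broader: "Oncology patients with castrate-resistant prostate cancer planned for therapy with abiraterone acetate or enzalutamide and prednisolone undergoing clinically indicated MDCT". The other four inclusion criteria cover age, creatinine, BMI and consent. The only exclusion is a previous contrast reaction. None requires a bone lesion, and Background & Significance says that castrate-resistant disease starts with "rising prostate-specific antigen (PSA) levels in the absence of metastases or symptoms".

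Section 5 (Data Analysis & Statistical Considerations) introduces the primary analysis as showing that one can "monitor metastatic bone disease in castration resistant prostate cancer more accurately than regular single energy CT, single phase dual energy CT" and bone scans. It plans iodine quantification with an ROC threshold, and blinded multi-reader "sensitivity and specificity for distinction between disease progression at first follow-up three month after initiation of therapy". It does not say whether the unit is the patient or the lesion, or which patients enter. The last sentence also names only one of the two classes to be distinguished.

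Other text bears on how that gap would be filled. Purpose of the Study says that "subclinical metastatic lesions may only become detectable at imaging in response to therapy". Background & Significance says that "patients with advanced disease have a very high incidence of bone metastases", that the two study drugs "improved survival significantly for patients with metastatic castration-resistant prostate cancer", and closes on the need to tell flare from progression.

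**The concern.** The objective and the enrolled population do not match, and no analysis set reconciles them. A man with no bone lesion on any scan cannot be called a bone progressor by any modality. If he is counted as a non-progressor, every modality scores a correct negative on him.

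Two things would follow. Reported specificity would exceed the specificity among men in whom flare and progression are hard to tell apart. The specificity advantage of dual energy CT over single energy CT or bone scan would also look smaller than it is in those men.

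The per-patient reading is not far-fetched. Design & Procedures says the three examinations serve to sort patients into partial remission, stable and progressive disease, and the PCWG3 rule cited in the background classifies a patient by counting new lesions.

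**Working it through.** **Nothing to reproduce.** The plan gives no expected accuracy, progression rate, power or precision. Its only count is the 150 men to be contacted (Consent Process). Every input below is therefore an assumption unless marked otherwise.

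**Identity.** Let w be the share of non-progressors who have no bone lesion, Sb the specificity in men with bone lesions and Sf the specificity in bone-free men.

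- Pooled specificity = w·Sf + (1 − w)·Sb, so the rise is w·(Sf − Sb).
- Pooled difference between two modalities = (1 − w)·D + w·d, where D is the difference in men with bone lesions and d the difference in bone-free men.

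If bone-free means no lesion on any compared modality, then Sf = 1 and d = 0. With Sb = 80% for dual energy CT and 60% for a comparator, D = 20 points:

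| w | Rise at Sb = 80% | Rise at Sb = 60% | Pooled difference |
|---|---|---|---|
| 5% | 0.05 × 20 = 1 | 0.05 × 40 = 2 | 0.95 × 20 = 19 |
| 10% | 2 | 4 | 18 |
| 20% | 4 | 8 | 16 |
| 30% | 6 | 12 | 14 |
| 40% | 8 | 16 | 12 |

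If bone-free instead means truly free of bone disease, false positives become possible. With Sf = 98%, the rise at w = 5% is 0.05 × 18 = 0.9 or 0.05 × 38 = 1.9 points. If the comparator is 5 or 10 points worse in these men, the pooled difference at w = 10% is 18 + 0.5 = 18.5 or 18 + 1 = 19, so there is less shrinkage.

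**From enrolled men to non-progressors.** Let f be the bone-free share of enrolled men and p the share of men with bone lesions who progress. Then w = f / [f + (1 − f)(1 − p)].

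- f = 5%: p = 20% gives 0.05/0.81 = 6.2%; p = 40% gives 0.05/0.62 = 8.1%. The 20-point difference becomes 18.8 or 18.4.
- f = 10%: 0.10/0.82 = 12.2%, or 0.10/0.64 = 15.6%.

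**The only frequency in the documents.** The background gives 65–75% with bone lesions at autopsy. Its complement, f = 25–35%, with p = 30% gives w = 0.25/0.775 = 32.3% and 0.35/0.805 = 43.5%. The 20-point difference would become 13.5 or 11.3. That figure describes prostate cancer patients in general, not men starting these two drugs. The passages on advanced and metastatic disease point to a smaller f.

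**What does not move.** Sensitivity uses progressors only. A lesion-level analysis has no entry for a man without lesions, and he offers no lesion in which to measure iodine for the ROC analysis. In a paired comparison he adds a concordant pair. Per 100 non-progressors at w = 20%, the 80 men with lesions give a net 0.20 × 80 = 16 discordant calls. Adding 20 concordant men leaves those 16 and the paired test unchanged; only the denominator of the difference grows (16/100).

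**Scale.** With 100 non-progressors and specificity near 70%, the standard error is √(0.7 × 0.3/100) = 4.6 points. The 1 to 2 point rise at w = 5% lies well inside that.

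**The case for a change.** The strongest argument for a change is that a low bone-free share is an expectation that no criterion enforces. Even at a share of zero, the unit and denominator of the primary sensitivity and specificity are unwritten, and settling them before the blinded reads would prevent a choice made after seeing results. The cost would be a short paragraph.

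The gap in the wording is real, and so is the dilution under that one reading. The step from there to a wrong result is weaker. It needs a per-patient unit, all enrolled men in the denominator and a material bone-free share, and the documents establish none of the three.

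Nor is the repair obvious:

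- Requiring a baseline lesion at entry would lose men whose lesions first show under treatment. It would also remove the lesion-free men who inform specificity for the baseline-detection objective.
- Restricting the analysis to men with a lesion on any compared modality, at baseline or first follow-up, would keep truly bone-free men only when some modality is falsely positive and drop the correctly negative ones. That lowers specificity selectively. It also ties membership to new lesions, which is close to the progression call itself.

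**Conclusion.** No change follows. The plan leaves out a definition; it does not state a rule that gives a wrong answer. The reader-study sentence omits its second class, but Purpose of the Study and Background & Significance supply it: flare or treatment response, set against progression in bone. A man who stays bone-free belongs to neither class. An analyst following the stated aim of monitoring metastatic bone disease would restrict the comparison to men with bone lesions or work by lesion, and would have to state the denominator to report a sensitivity at all.

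If the broad per-patient reading were used anyway, a 5% bone-free share of non-progressors would raise specificity by about 1 to 2 points and turn a 20-point difference into 19. Larger shares do more, down to 12 points at 40%, but nothing in the documents supports such a share for men starting these drugs. With every modality negative in these men, the distortion shrinks the apparent gain from dual energy CT and cannot create or reverse one. Broad eligibility also serves the baseline-detection, soft-tissue and lymph-node objectives, and the study is a feasibility pilot with no confirmatory test.

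This rests on assumed specificities of 60% and 80% and on the bone-free share being small, which the protocol suggests but does not quantify.
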